5.5 Analysis of Safety

The analyses of safety is done for the open-label safety analysis set and the safety analysis set.

5.5.1 Exposure

Duration of exposure will be summarised as described in the protocol section 11.3.3.1. If the date of last application of IMP is missing, the date of last visit attended by the subject will be used instead.

Patient years of exposure during a trial phase will be calculated as exposure during the relevant phase (accounting for both maintenance and rescue IMP as relevant) divided by 365.25.

The amount of IMP used will be summarised for the open-label treatment phase. For each subject the amount of IMP used will be normalised by the length of the open-label phase.

The total amount of IMP used, and the amount of rescue IMP used will be summarised by treatment group for the maintenance phase. For each subject the total amount of IMP and the amount of IMP used will be normalised by the length of maintenance phase or the total time in relapse, respectively.

The amount of IMP used, and the amount of rescue will not be summarised for each visit interval as described in the protocol. Instead a cumulative plot of the amount of IMP used over time during the maintenance phase by each subject together with an average cumulative amount curve will be done for the safety analysis set. The cumulative amount of IMP for each subject will be normalised by time in the maintenance phase (in days). The cumulative

Trial ID: LP0053-1004	Date: 15-JUL-2019	Version: 1.0 Page 30 of 177
-----------------------	-------------------	--------------------------------

amount of IMP used up to each scheduled visit and the corresponding number of subjects contributing to these amounts will be tabulated by treatment group.

More details for the tables and listings can be found in [Appendix I](#) and [Appendix II](#).

5.5.2 Drug Accountability

For each subject, the weight of IMP used for a given trial period will be calculated as the difference between the weight of a set of full cans dispensed and the weight of the returned cans. The weight of cans dispensed to a subject will be the mean weight of a full can multiplied by the number of dispensed cans. The mean weight of a full can is 195.52 g based on the weight of 20 cans. The weight of IMP used will be multiplied by a correction factor of 0.41 to account for the propellant gasses.

If cans are returned with their seal unbroken, the weight of IMP used from that bottle will be assigned a value of zero. If a returned can weigh more than the estimated mean weight of a full can, it will be assumed that zero grams were used from that can.

If cans are returned at a wrong visit the amount of IMP used from these cans will be assumed to be used in the period from the cans being dispensed to the cans being returned. If some cans are not returned at all, these cans are assumed to be emptied by the subjects. The amount of IMP used for that bottle will be assigned a value of 60 g, which is the approved amount of IMP contained in an individual can.

In the case where cans are not returned due to the subjects being lost to follow up after the cans are dispensed, the amount of IMP used from these cans will not be calculated, as the subject is assumed to end the treatment with IMP after withdrawal from the trial.

5.5.3 Adverse Events

The adverse events (AEs) will be assigned to a specific period (e.g. open-label phase or randomised phase) based on the onset date the AE.

The long-term safety of LEO 90100 will be evaluated based on data from the randomised phase.

For treatment emergent adverse events (hereafter referred to as AEs) occurring in the randomised phase the following tables will be done:

Trial ID: LP0053-1004	Date: 15-JUL-2019	Version: 1.0 Page 31 of 177
-----------------------	-------------------	--------------------------------

An overall summary of AEs, SAEs, premature discontinuation from the trial due to AEs, treatment related AEs, severity of AEs, action taken with IMP and outcome of AEs will be presented. The summary will include number of events, number (percentage) of subjects and exposure rates.

The number of AEs, the number and percentage of subjects experiencing each type of AE, and the exposure rate will be tabulated by SOC and preferred term. The tabulation will be done for all treatment emergent AEs, for each type of severity separately, for related AEs, for serious AEs (SAEs), for non-serious adverse events, and for frequent AEs ($\geq 1\%$ in any treatment group).

All above tables will be done for the safety analysis set by treatment for the first 28 weeks of the randomised phase, and for the remaining 32 weeks of the randomised phase separately. In addition, the tables will be done for the safety analysis set by randomised treatment and rescue IMP for the total randomised phase, for the first 28 weeks of the randomised phase, and for the remaining 32 weeks of the randomised phase separately.

Further details for the tables can be found in [Appendix I](#) and [Appendix II](#).

Open-label phase:

For completeness, AEs for the open-label phase will be summarised separately as follows:

An overall summary of AEs, SAEs, AEs leading to withdrawal, treatment related AEs, severity of AEs, action taken with IMP and outcome of AEs will be presented. The summary will include number of events, number (percentage) of subjects and exposure rates.

The number of AEs, the number and percentage of subjects experiencing each type of AE, and the exposure rate will be tabulated by SOC and preferred term. The tabulation will be done for all treatment emergent AEs, for each type of severity separately, for related AEs, for serious AEs (SAEs), for non-serious adverse events, and for frequent AEs ($\geq 1\%$).

The causal relationship to trial medication for each type of AE will be tabulated by SOC and preferred term.

All above tables will be done for the open-label safety analysis set.

Additional summaries in the maintenance phase:

Tables exploring safety profile while in remission or relapse will be presented based on the treatment emergent adverse events occurring in the maintenance phase.

Trial ID: LP0053-1004	Date: 15-JUL-2019	Version: 1.0 Page 32 of 177
-----------------------	-------------------	--------------------------------

For AEs from the maintenance phase the following tables will be done:

The number of AEs, the number and percentage of subjects experiencing each type of AE, and the exposure rate will be tabulated by SOC and preferred term. The tabulation will be done for all treatment emergent AEs, for each type of severity separately, for related AEs, for serious AEs (SAEs), for non-serious adverse events, and for frequent AEs ($\geq 1\%$ in any treatment group). The causal relationship to treatment regimen for each type of AE will be tabulated by SOC and preferred term.

All above tables will be done for the safety analysis set by treatment for the first 28 weeks of the maintenance phase, and for the remaining 24 weeks of the maintenance phase separately. In addition, the tables will be done for the safety analysis set by randomised treatment and rescue IMP for the total maintenance phase, for the first 28 weeks of the maintenance phase, and for the remaining 24 weeks of the maintenance phase separately.

All non-treatment emergent AEs will be listed.

Further details for listings can be found in [Appendix I](#).

Statistical tests:

In the protocol it is described that the percentage of subjects with any AE or with any related AE will be compared between treatment groups by a chi-square test or Fisher's exact test (if expected cell count < 5). However, this analysis will most likely be biased towards different drop-out between the treatment groups. The longer a subject is followed, the greater is the chance of observing an AE for the subject. As the number of early withdrawals might differ considerably between the two treatment groups, statistical tests performed on the percentage of subjects with any AE or with any related AE is not appropriate in this set up. Hence, no statistical testing will be done for AEs.

Calculation of AE rate:

The AE rate will be calculated as number of AEs divided by patient years of exposure in the different phases multiplied by 100.

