11.3.3 Exposure and Treatment Compliance

11.3.3.1 Exposure

The duration of exposure to treatment in a specific visit interval will be calculated as the number of days from date of first application of IP in that period to the date of last application of IP in that period, both days included.

Duration of exposure during the open-label treatment phase will be summarized for the open-label treatment phase safety analysis set.

Duration of exposure during the maintenance phase will be summarized by treatment group for the maintenance phase safety analysis set.

For each subject, the weight of IP used for each visit interval will be determined by calculating the difference between the weight of a set of full cans dispensed and the weight of the returned cans.

The amount of IP used will be summarised for the total open-label treatment phase for the open-label treatment phase safety analysis set.

The amount of IP used will be summarised by treatment group for each visit interval and for the total maintenance phase for the maintenance phase safety analysis set.

The amount of rescue medication used will be summarised by treatment group for each visit interval and for the total maintenance phase for the maintenance phase safety analysis set.

The total amount of IP and rescue medication used will be summarised by treatment group for each visit interval and for the total maintenance phase for the maintenance phase safety analysis set.

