5.1 Definition of trial periods

The trial periods are defined in [Table 1](#).

Table 1: Definition of trial periods

Trial period	Definition
Open-label phase	From the day of enrolment to the day before randomisation.
Randomised phase	From the day of randomisation to end of trial, both days included.
Maintenance phase	From the day of first exposure to maintenance IMP to the last day of exposure (rescue or maintenance IMP), both days included.
Follow-up phase	From the day after last application of maintenance or rescue IMP to end of trial.
Relapse period	Relapse is defined as a PGA score of at least 'mild' during the maintenance phase, for details on relapse see CTP section 6.14.1. A relapse period is defined from the relapse start day (included) to the

	visit date when relapse treatment is discontinued (not included).
Remission period	A remission period is a period where the subject is not in a relapse period within the maintenance phase.
Visit interval	The interval between two successive scheduled visits.

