Recovered/Resolved with sequelae	xxx	(xx.x)	xxx	xxx.x	xxx	(xx.x)	xxx	xxx.x
Unknown	xxx	(xx.x)	xxx	xxx.x	xxx	(xx.x)	xxx	xxx.x

AEs collected during the exposure time in the <total/first 28 weeks of the/remaining 24 weeks of the> maintenance phase are shown.
 IMP: Investigational medicinal product, PYE: Patient years of exposure, N: Number of subjects with one or more events, %: Percentage of subjects with one or more events, E: Number of adverse events, R: Rate (number of adverse events divided by patient years of exposure multiplied by 100).

1) Considered possibly or probably related to IMP by the investigator.

Shell 61: Overall summary of adverse events during <XXX> by randomised treatment and rescue medication: safety analysis set

	LEO 90100 remission (n=xxx)			Vehicle remission (n=xxx)			LEO 90100 relapse (n=xxx)			Vehicle relapse (n=xxx)		
	N	(%)	E	R	N	(%)	E	R	N	(%)	E	R
PYE	xxx.xx			xxx.xx			xxx.xx			xxx.xx		
Events	xxx (xx.x)	xxx	xxx.x	xxx (xx.x)	xxx	xxx.x	xxx (xx.x)	xxx	xxx.x	xxx (xx.x)	xxx	xxx.x
Serious	xxx (xx.x)	xxx	xxx.x	xxx (xx.x)	xxx	xxx.x	xxx (xx.x)	xxx	xxx.x	xxx (xx.x)	xxx	xxx.x
Severity												
Mild	xxx (xx.x)	xxx	xxx.x	xxx (xx.x)	xxx	xxx.x	xxx (xx.x)	xxx	xxx.x	xxx (xx.x)	xxx	xxx.x
Moderate	xxx (xx.x)	xxx	xxx.x	xxx (xx.x)	xxx	xxx.x	xxx (xx.x)	xxx	xxx.x	xxx (xx.x)	xxx	xxx.x
Severe	xxx (xx.x)	xxx	xxx.x	xxx (xx.x)	xxx	xxx.x	xxx (xx.x)	xxx	xxx.x	xxx (xx.x)	xxx	xxx.x
Related ¹ to IMP	xxx (xx.x)	xxx	xxx.x	xxx (xx.x)	xxx	xxx.x	xxx (xx.x)	xxx	xxx.x	xxx (xx.x)	xxx	xxx.x
Leading to withdrawal from trial	xxx (xx.x)	xxx	xxx.x	xxx (xx.x)	xxx	xxx.x	xxx (xx.x)	xxx	xxx.x	xxx (xx.x)	xxx	xxx.x
Action taken with IMP												
Dose not changed	xxx (xx.x)	xxx	xxx.x	xxx (xx.x)	xxx	xxx.x	xxx (xx.x)	xxx	xxx.x	xxx (xx.x)	xxx	xxx.x
Drug withdrawn	xxx (xx.x)	xxx	xxx.x	xxx (xx.x)	xxx	xxx.x	xxx (xx.x)	xxx	xxx.x	xxx (xx.x)	xxx	xxx.x
Not applicable	xxx (xx.x)	xxx	xxx.x	xxx (xx.x)	xxx	xxx.x	xxx (xx.x)	xxx	xxx.x	xxx (xx.x)	xxx	xxx.x
Unknown	xxx (xx.x)	xxx	xxx.x	xxx (xx.x)	xxx	xxx.x	xxx (xx.x)	xxx	xxx.x	xxx (xx.x)	xxx	xxx.x
Outcome												
Fatal	xxx (xx.x)	xxx	xxx.x	xxx (xx.x)	xxx	xxx.x	xxx (xx.x)	xxx	xxx.x	xxx (xx.x)	xxx	xxx.x
Not recovered/Not resolved	xxx (xx.x)	xxx	xxx.x	xxx (xx.x)	xxx	xxx.x	xxx (xx.x)	xxx	xxx.x	xxx (xx.x)	xxx	xxx.x
Recovering/Resolving	xxx (xx.x)	xxx	xxx.x	xxx (xx.x)	xxx	xxx.x	xxx (xx.x)	xxx	xxx.x	xxx (xx.x)	xxx	xxx.x

continued...

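### As SAP 5.1, 5.5.1 and 5.5.3 read, adverse event rates for the total randomised phase and its last 32 weeks count follow-up events but divide by exposure that ends at the last application, and the shell footnotes contradict this

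*SAP*

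**What the plan says.** SAP 5.1 defines three periods that matter here:

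- The randomised period is dated "From the day of randomisation to end of trial, both days included", and so takes in the follow-up.
- The maintenance period is dated "From the day of first exposure to maintenance IMP to the last day of exposure (rescue or maintenance IMP), both days included", and so leaves the follow-up out.
- The follow-up itself is dated "From the day after last application of maintenance or rescue IMP to end of trial", and so contains no applications.

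SAP 5.5.3 assigns each adverse event (AE) to a phase by its onset date and bases the long-term safety evaluation on the randomised phase. It tabulates the first 28 weeks and then, in its words, "for the remaining 32 weeks of the randomised phase separately". For the maintenance phase the same section splits the time into 28 and 24 weeks.

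Protocol 9.1 has AEs collected up to the FU3 visit, which Protocol 6.1.5 places 8 weeks after the end of treatment. Protocol 11.3.6.1 defines treatment emergence by a start after the first application and sets no closing date.

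The rate is defined in SAP 5.5.3: "The AE rate will be calculated as number of AEs divided by patient years of exposure in the different phases multiplied by 100". Its denominator comes from SAP 5.5.1: "Patient years of exposure during a trial phase will be calculated as exposure during the relevant phase". That section takes the duration of exposure from Protocol 11.3.3.1, where it is "calculated as the number of days from date of first application of IP in that period to the date of last application".

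The footnote under Shells 60, 63 and 66 in SAP Appendix II reads: "AEs collected during the exposure time in the <total/first 28 weeks of the/remaining 24 weeks of the> maintenance phase are shown". These are the shells for the tables by randomised treatment.

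**The concern.** Time in follow-up can add events to the numerator of a randomised-phase rate but adds nothing to the denominator, because no investigational product is applied then (Protocol 7.8.3). Some follow-up events are expected by design: rebound after stopping treatment must be reported as an AE (Protocol 9.3.6). Off-treatment events would therefore be charged to on-treatment time.

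The rates matter more than usual in this trial. SAP 5.5.3 drops the planned AE tests because percentages would be distorted if withdrawal differs between arms. That leaves the exposure-based rates as the comparison that adjusts for unequal follow-up, so their time base should be sound. The mismatch also need not cancel between arms: the shorter the exposure, the larger the share that 8 weeks of follow-up represents.

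**Working it through.** **Windows.** 28 + 32 = 60 weeks and 52 + 8 = 60 weeks, so the randomised-phase split includes the follow-up. 28 + 24 = 52 weeks, so the maintenance-phase split does not.

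**Reproducing the plan's drop-out figures (Protocol 11.1).** With 30% exponential drop-out over 52 weeks, λ = −ln(0.7)/52 = 0.00686 per week.

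- 380 × exp(−22λ) = 326.8 (stated 326).
- 380 × exp(−48λ) = 273.4 (stated 273).
- ln(2)/λ = 101.05 weeks (stated about 101).

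**Factor at an equal event rate.** Let T be weeks of exposure, capped at 52, with 8 further weeks of observation for every subject. If events occur in follow-up at the on-treatment rate, the stated rate is multiplied by observation time divided by exposure time in the window. Write S(t) = exp(−λt), so S(20) = 0.872, S(28) = 0.825 and S(52) = 0.700.

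- Total phase: mean exposure = (1 − 0.7)/λ = 43.7 weeks; (43.7 + 8)/43.7 = 1.18.
- First 28 weeks: exposure = (1 − S(28))/λ = 25.5; observation = 8 + (1 − S(20))/λ = 26.7; ratio 1.05.
- Last 32 weeks: exposure = (S(28) − 0.7)/λ = 18.3; observation = (S(20) − 0.7)/λ = 25.0; ratio 1.37.

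A simulation of 2,000,000 subjects gives the same factors and the other rows below.

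| Drop-out over 52 weeks | Total phase | First 28 weeks | Last 32 weeks |
|---|---|---|---|
| 0% | 60/52 = 1.154 | 1.000 | 32/24 = 1.333 |
| 30% (protocol) | 1.183 | 1.048 | 1.372 |
| 50% (assumption) | 1.213 | 1.094 | 1.411 |

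**Lower event rate in follow-up (assumption).** If the follow-up rate is a fraction q of the on-treatment rate, the factor is 1 + q × (factor − 1). For the total phase at 30% drop-out this gives 1.00 at q = 0, 1.046 at q = 0.25, 1.091 at q = 0.5 and 1.183 at q = 1.

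**Less follow-up in drop-outs (assumption).** If only the 70% who complete contribute follow-up, the added time is 0.7 × 8 = 5.6 weeks per randomised subject. At an equal event rate the factors become 1 + 5.6/43.7 = 1.13 for the total phase and 1 + 5.6/18.3 = 1.31 for the last 32 weeks.

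**Difference between arms (assumptions, equal event rate in follow-up).**

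- Mean exposure 44 weeks on LEO 90100 and 36 on vehicle: 52/44 = 1.182 and 44/36 = 1.222; 1.222/1.182 = 1.034.
- Drop-out 30% on LEO 90100 and 60% on vehicle: 1.183 and 1.235; 1.235/1.183 = 1.044.

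**Footnotes against titles.** The footnote offers three windows: total, first 28 weeks and remaining 24 weeks, all of the maintenance phase. Most titles for the second window by randomised treatment (for example Tables 3-4, 3-11 and 3-53) name 32 weeks of the randomised phase, an option the footnote lacks. Table 3-2 is titled for the maintenance phase, although its companions 3-3 and 3-4 are for the randomised phase. Table 3-39 gives 24 weeks for the randomised phase.

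**The case against.** The strongest reply is that the shells already state a matched rule. If only AEs arising during maintenance-phase exposure are shown, numerator and denominator agree and the factor is exactly 1.00. On that view the documents show an inconsistency, not a bias. This stands in part: nothing in the documents establishes that the rates will be wrong, because the programmer could follow the footnotes. But the footnotes cannot be completed for a 32-week table, and following them would drop follow-up events that SAP 5.5.3 places in the phase. They conflict with the text and do not correct it.

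The second reply concerns size, and it stands. Equality of event rates is an assumption. Ascertainment may be thinner after treatment: the open AE question is specified for treatment-phase visits (Protocol 9.1), FU1 and FU2 are conditional, and FU3 may be a telephone contact. Subjects who die, withdraw consent or are lost may contribute little follow-up. For the stated drop-out, 1.18 and 1.37 are therefore upper values unless events become more frequent after stopping.

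A reader might also infer that every long-term safety rate is too high, or that rates are the only safety summary by arm. The documents support neither. The remission and relapse tables pair maintenance-phase events with maintenance-phase exposure. The first-28-week rates are untouched for anyone still on treatment at week 28. Event counts and subject percentages are tabulated by arm without this denominator, and rebound, local tolerability, ACTH and laboratory results are summarised separately. Shells 60 and 63 also print patient-years and event counts beside each rate, so the denominator is visible.

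**Conclusion.** The point holds for the randomised-phase rates as the SAP text defines them, mainly those for the total phase and the last 32 weeks. With the protocol's drop-out and 8 weeks of follow-up for all, the total-phase rate is overstated by between nothing and about 18%, depending on how often events start in follow-up. At an equal rate the overstatement is up to about 5% in the first 28 weeks and about 37% in the last 32.

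If vehicle subjects withdraw earlier, the vehicle rate is inflated about 3–4% more than the active rate under the differences assumed above, which would make LEO 90100 look slightly safer by comparison. Neither the follow-up event rate nor withdrawal by arm is given, so this is a range and not an estimate. The contradiction between text, titles and footnotes needs no assumption. The plan should be corrected because two programmers could follow it in good faith and report different rates.

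**What to change.** Choose one rule for the randomised-phase tables and state it in SAP 5.5.3:

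- divide by patient-years of observation, from randomisation to end of trial, cut to the window shown; or
- restrict the numerator to AEs with onset during exposure, and report follow-up AEs separately.

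The first keeps follow-up events in the long-term evaluation, as the present text intends. The second is closer to the shell footnotes. Keep patient-years of exposure for the maintenance-phase tables under either rule.

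Then align the 5.5.3 wording, the titles of Tables 3-2 and 3-39, and the footnotes of Shells 60, 63 and 66 with the choice. The cost is SAP wording and, for the first option, one derived variable. No data collection changes. Any rate that would have counted follow-up events over exposure time alone becomes lower.

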5.5.3.1 Adverse events associated with long term corticosteroid use

Adverse events associated with long term corticosteroid use will be presented as described in the protocol.

Trial ID: LP0053-1004	Date: 15-JUL-2019	Version: 1.0 Page 33 of 177
-----------------------	-------------------	--------------------------------

5.5.4 Rebound

Rebounds will be defined as described in the protocol. The baseline value will be the m-PASI value measured at the start of the rebound follow-up period. A rebound follow-up period is defined as either (i) 2 months after discontinuation of open-label phase treatment, (ii) 2 months after discontinuation of relapse treatment, or (iii) 2 months after discontinuation of maintenance treatment (up to Visit FU3).

Number of rebounds occurring within the first 2 months after discontinuation of the open-label phase treatment, and number of rebounds occurring within 2 months after discontinuation of relapse treatment will be summarised by treatment group.

Number of rebounds occurring within two months after discontinuation of maintenance treatment will be summarised by treatment group.

Cases of rebounds will be listed.

More details for the tables and listings can be found in [Appendix I](#) and [Appendix II](#).

